If the dose is reduced during the course of the study, the participant will continue the lowered dose for the remainder of the study. If adverse events do not improve within 14 days of lowering the dose, the investigational product may be permanently discontinued at the discretion of the treating study physician, participant, and participant's guardian. If a participant exhibits extreme exacerbation of behavioral symptoms (such as self-injurious behavior or aggression) that do not improve substantially following a dose reduction and are determined "probably" or "definitely" related to taking the investigational product, the investigational product may be permanently discontinued sooner than 14 days post-reduction, and the DSMB will be notified. As individuals with ASD often have cyclical changes in behavior independent of medication effects, the study staff will rely on caregivers' experience with the participant to determine if any observed behavior changes are within the expected range for that individual. If the investigational product is stopped permanently, the participant and his caregiver will be asked to complete the remainder of the study visits, return any unused study drug, and repeat safety lab studies.

2 Study Objectives

Primary Objective:

The primary objective of this clinical trial is to determine if Avmacol[®] is superior to placebo for improving social communication impairment in adolescent and young adult men with moderate to severe autism spectrum disorder (ASD), as measured by change in Social Responsiveness Scale-2 (SRS-2) [100] total scores.

Secondary Objectives:

Secondary objectives include: (1) assessing the safety and tolerability of Avmacol[®] in subjects with ASD; and (2) characterizing the effects of Avmacol[®] on behavioral challenges commonly associated with ASD, including hyperactivity, irritability, repetitive behavior, and inappropriate speech.

Exploratory Objectives:

In a subset of 30 participants, exploratory objectives include: (1) Assessment of gut micobiota diversity and relative abundance of microbial species from fecal samples collected before and after 12 weeks of treatment with sulforaphane or placebo. (2) Explore the relationship between changes in microbiota composition and behavioral outcomes in young men treated with sulforaphane or placebo.

3 Study Design

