3.2 Primary Safety Endpoints

- CBC with differential, actual values and percent change in values from Screening visit to Week 12 visit.
- CMP (Na, K, Cl, CO2, BUN, Cr, Ca, Mg, Ph, glucose), actual values and percent change in values from Screening visit to Week 12 visit.
- LFTs (Total bilirubin, AST, ALT), actual values and percent change in values from Screening visit to Week 12 visit.
- TSH, actual value and percent change in value from Screening visit to Week 12 visit.
- Vital signs (weight, height, blood pressure, and heart rate), actual values at each time point measured and percent change in values from Baseline to Week 12 visit (the end of the active treatment phase)
- Physical Examination, general assessment of health at Screening visit and at Week 12 visit (the end of the active treatment phase)
- Mean (%) relative abundance of microbial phyla and genera in fecal samples at Baseline and Week 12.
- Percent change in Bacteroidetes to Firmicutes (B:F) ratio in fecal samples from Baseline to Week 12.
- Change in alpha diversity ("within-sample") metrics (the absolute number of operational taxonomic units (OTUs), Chao1 estimator, and Shannon index) in microbiota from Baseline to Week 12.
- Change in beta diversity ("between-sample") metrics (Bray-Curtis dissimilarity, Weighted Unifrac distance, and Unweighted Unifrac distance) in microbiota from Baseline to Week 12.

4 Subject Selection and Withdrawal

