Similar GLMM analyses will be conducted to examine the longitudinal assessments of CGI Severity and RBSR and of subscales if the total scores show treatment impacts.

Exploratory Hypotheses

We hypothesize that treatment with sulforaphane will result in greater diversity of gut microbial species and a higher ratio of Bacteroidetes to Firmicutes spp. compared to placebo, and that these alterations in gut microbiota will be positively associated with behavioral improvements in the sulforaphane treatment group.

We will utilize Genotek's validated wet-lab and metagenomic data analytic pipeline for the batched sample processing and data analysis. Microbial DNA will be extracted and amplified using PCR, and 16S rRNA gene sequencing will be performed using the Illumina MiSeq platform. A curated taxonomic database will be used to assign a taxonomic classification to the sequencing reads. The mean (%) relative abundance of microbial phyla and genera will be calculated for the sulforaphane and placebo groups pre- and posttreatment. The percent change in Bacteroidetes to Firmicutes (B:F) ratio from baseline to endpoint will be compared between treatment groups using Analysis of Covariance (ANCOVA), with baseline B:F ratio included as a covariate.

Microbiota diversity and relative abundance will be assessed using conventional within sample ("alpha diversity") and between-sample ("beta diversity") metrics. Three metrics will be used to assess change in alpha diversity over time: the absolute number of operational taxonomic units (OTUs), Chao1 estimator, and Shannon index. We will use ANCOVA to test for significant differences in alpha diversity from baseline to endpoint within each treatment group. Beta diversity will be assessed with 3 metrics: Bray-Curtis dissimilarity, Weighted Unifrac distance, and Unweighted Unifrac distance. These indices will be used to determine the variance in an individual over time and the mean dissimilarity between individuals in each group. Weighted Unifrac distance distance will be used for Principal Coordinates Analysis (PCoA). We will create a PCoA plot to visually identify whether samples from each treatment group cluster together at different time points (before and after treatment). This can help determine whether any changes identified during beta diversity analysis are directed changes or random noise.

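### Section 7.2 hypothesises greater gut diversity than on placebo, but tests alpha diversity only within each arm

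*Combined protocol and SAP*

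**What the plan says.** Section 2 introduces the microbiota work with "In a subset of 30 participants, exploratory objectives include" and describes it as an assessment of "fecal samples collected before and after 12 weeks of treatment with sulforaphane or placebo".

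Section 7.2 (Exploratory Hypotheses) makes this a directional claim against placebo. Sulforaphane is expected to give "greater diversity of gut microbial species and a higher ratio of Bacteroidetes to Firmicutes spp. compared to placebo". The two halves are then analysed differently:

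- **B:F ratio:** the percent change in "ratio from baseline to endpoint will be compared between treatment groups using Analysis of Covariance (ANCOVA"), with the baseline ratio as covariate.
- **Alpha diversity (OTU count, Chao1, Shannon):** "We will use ANCOVA to test for significant differences in alpha diversity from baseline to endpoint within each treatment group".

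Beta-diversity indices are to describe "the variance in an individual over time and the mean dissimilarity between individuals in each group". Ordination is read by eye: "We will create a PCoA plot to visually identify whether samples from each treatment group cluster together at different time points".

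**The concern.** The hypothesis is a statement about the difference between arms. A test of change inside one arm does not estimate that difference. It answers whether diversity moved over 12 weeks among those on sulforaphane, and separately whether it moved among those on placebo. Diet, season, repeat sampling or regression to the mean could move both arms together.

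Followed as written, the plan leaves the diversity half without a prespecified test. It also leaves open, once the data are seen, which contrast is reported. A reader could be tempted to take a significant change on sulforaphane beside a non-significant one on placebo as a treatment effect. The plan does not say it will do this, but it offers nothing better for alpha diversity.

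**Working it through.** **1. Is the contrast supplied elsewhere?** The argument rests on the text, and the plan states no figure for alpha diversity to reproduce.

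| Place | Content | Between-arm test of diversity? |
|---|---|---|
| Section 2, exploratory objectives | Assessment before and after treatment; relation to behaviour | No |
| Section 3.1 | Timing of stool collection | No |
| Section 3.2 | Change in alpha metrics ("Chao1 estimator, and Shannon index) in microbiota from Baseline to Week 12") and in beta metrics | No arm comparison named |
| Section 7.1 | Power for B:F only, 15 per group | No |
| Section 7.2, mixed models | Primary and secondary hypotheses | No |
| Section 7.2, alpha diversity | ANCOVA inside each arm | No |
| Section 7.2, beta diversity and PCoA | Within-person and within-group description; visual plot | No, and not a measure of within-sample diversity |
| Section 7.2, last paragraph | Microbiota change against behaviour change | No |
| Section 7.3 | Analysis population, missing data | No |

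The B:F paragraph says between groups and the alpha-diversity paragraph after it says within each group. The missing contrast is established without any calculation.

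**2. What could reading the two arms side by side do? (illustration)** The plan states none of these assumptions: a pre-post t-test in each arm, two-sided 0.05, and the rule that a significant rise on sulforaphane with no significant change on placebo means efficacy. There is no true treatment effect; both arms drift by δ SD of change.

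With n = 15, df = 14 and critical t = 2.145, let U = P(significant rise) and T = P(significant in either direction), from the noncentral t with noncentrality δ√15. The false-positive rate per metric is U × (1 − T).

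| δ | U | U × (1 − T) |
|---|---|---|
| −0.25 | 0.002 | 0.2% |
| 0 | 0.025 | 2.4% |
| 0.10 | 0.055 | 5.1% |
| 0.25 | 0.145 | 12.4% |
| 0.54 | 0.495 | 25.0% (maximum) |
| 0.80 | 0.821 | 14.7% |
| 1.00 | 0.949 | 4.8% |
| 1.50 | 0.9997 | 0.03% |

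Example at δ = 0.25: T = 0.1453 + 0.0021 = 0.147, so 0.145 × (1 − 0.147) = 0.124. The rate exceeds 5% only for δ between 0.096 and 0.995. In simulation (40,000 trials per drift value, baseline correlation 0.5), a between-arm ANCOVA rejected in 4.8% to 5.1% of trials at every drift tried from −0.25 to +1.1 SD. That counts both directions; the share favouring sulforaphane is about half, near 2.5%.

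**3. What would the between-arm test deliver?** Two-sided 0.05 assumed.

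- 15 per arm, df 28, unadjusted: half-width = 2.048 × √(2/15) = 0.748 SD of change. Power is 26% at 0.5 SD and reaches 80% at 1.06 SD.
- If the 15% loss assumed in Section 7.1 for the main sample also applied here (15 × 0.85 = 12.75, taken as 13 per arm, df 24): 2.064 × √(2/13) = 0.810 SD. Power is 23% at 0.5 SD and reaches 80% at 1.15 SD.
- Baseline-adjusted, 15 per arm, residual SD √(1 − r²), df 27: 80% power at 0.92 SD of the Week 12 value for r = 0.5, or 0.76 SD for r = 0.7 (correlations assumed).
- Three unadjusted metrics: family-wise error 1 − 0.95³ = 14.3% if independent, about 11% if correlated at 0.7 (assumed).

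**The case against.** The strongest reply is that this is a drafting slip. An ANCOVA confined to one arm has no group factor, the same method is used between groups one paragraph earlier, and the hypothesis is framed against placebo. A between-arm model may well have been meant. That is plausible, but the plan has to be judged on its wording, and the two phrases contrast directly. If it is a slip, correcting it is all the more straightforward.

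The error rates in step 2 can fairly be discounted. They depend on a rule, a test and drift values that the plan does not contain. They also count only results favouring sulforaphane, so the like-for-like benchmark is about 2.5%, which the rule exceeds from just above 0 to about 1.09 SD. The fall in the rate at large drift depends on requiring a non-significant placebo arm. If a significant rise on sulforaphane alone were taken as an effect, the error would be U itself, which is 95% at 1.0 SD. The rates are an illustration and carry no weight in the conclusion.

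Two further points do not change it. Section 3.2 lists diversity under a safety heading, but no safety rule or planned safety review uses it, and Section 2 calls the objective exploratory. Analysing the Week 12 value where Section 3.2 speaks of change makes no difference: with baseline as covariate, both give the same treatment estimate.

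The low stakes are conceded. The subset is small, no decision hangs on the result, and the added test would resolve only large effects.

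**Conclusion.** The concern holds, as a minor point. The diversity half of the exploratory hypothesis is stated against placebo and has no between-arm test anywhere in the document. This follows from the text and rests on no numerical assumption. Its reach is one half of one exploratory hypothesis in 30 participants; the primary and secondary efficacy analyses and the safety rules are unaffected.

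Any inflation of false positives is conditional on an interpretation that the plan does not state and on a shared upward drift of unknown size.

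**What to change.** Replace the alpha-diversity sentence in Section 7.2 with wording such as:

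> For each alpha-diversity metric (OTU count, Chao1, Shannon), the Week 12 value will be compared between treatment groups by ANCOVA with the baseline value as covariate. The adjusted between-group difference and its 95% CI will be reported for all three metrics. Within-group changes will be summarised descriptively. These results are exploratory and are not adjusted for multiplicity.

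Age stratum, the randomisation stratum, may be added as a covariate. If only a within-arm description is intended, reword the hypothesis so that diversity is no longer claimed relative to placebo.

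The cost is one sentence, with no new samples, visits or assays. The drawback is the wide interval shown above, which is a reason to report the estimate with its CI. The exploratory label is needed because three metrics are tested without adjustment.

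### Change in beta diversity is a listed endpoint, but no between-arm comparison is given, and a plot read by eye is the only stated aid for telling directed change from noise

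*Combined protocol and SAP*

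**What the plan says.** Section 3.2, headed Primary Safety Endpoints, includes change in beta-diversity "metrics (Bray-Curtis dissimilarity, Weighted Unifrac distance, and Unweighted Unifrac distance) in microbiota from Baseline to Week 12". Elsewhere the microbiota work is exploratory. Section 2 introduces it with "In a subset of 30 participants, exploratory objectives include", section 7.1 calls the analysis exploratory, and section 7.2 places it under Exploratory Hypotheses. The hypothesis there is comparative against placebo: "We hypothesize that treatment with sulforaphane will result in greater diversity of gut microbial species", together with a higher Bacteroidetes to Firmicutes (B:F) ratio.

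For beta diversity, section 7.2 plans two things.

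- **Numerical summaries:** "These indices will be used to determine the variance in an individual over time and the mean dissimilarity between individuals in each group".
- **A principal coordinates (PCoA) plot based on Weighted Unifrac:** "We will create a PCoA plot to visually identify whether samples from each treatment group cluster together" before and after treatment. Of this plot it says: "This can help determine whether any changes identified during beta diversity analysis are directed changes or random noise".

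In the same section the B:F ratio has an ANCOVA between arms with baseline as covariate. Alpha diversity has an ANCOVA, worded as within each arm. The closing paragraph of 7.2 relates microbiota change to behavioral change by mixed models. Section 7.1 claims power, at 15 per group, for the B:F ratio only.

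**The concern.** Whether a change is directed or is noise is an inferential question. It needs a comparison with what chance alone would produce. Section 7.2 gives no such comparison for beta diversity: the numbers it plans are not contrasted between arms, and the plot has no reference distribution. A PCoA plot also shows only part of the variation, on its leading axes. Two of the three metrics do not enter the plot at all.

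What is at stake is one exploratory conclusion. A report could describe the arms as clustering apart, or as not doing so, on a judgement that another analyst could not reproduce and that carries no stated chance of error.

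**Working it through.** **1. Is a between-arm test named anywhere?** Sections 2, 3.2, 7.1 and 7.2, set side by side:

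| Measure | Numerical analysis | Arms compared? | Level or power stated? |
|---|---|---|---|
| B:F ratio | ANCOVA, baseline as covariate | Yes | Power over 80% at 15 per group (7.1) |
| Alpha diversity, 3 metrics | ANCOVA | Worded within arm | No |
| Beta diversity, 3 metrics | Within-person variance; within-group mean dissimilarity | No | No |
| Microbiota and behavior | Mixed models for association | Not on beta diversity | No |

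The 5% level in 7.2 belongs to the overall SRS-2 test. The documents state no figure for beta diversity, so there is none to reproduce.

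**2. Can the planned summaries show direction?**

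- *Within a person.* Each participant has two samples a distance d apart. Each lies d/2 from their midpoint, so the sum of squares is 2 × (d/2)² = d²/2. The within-person variance therefore depends only on that one distance. It measures how far he moved, not which way.
- *Within a group.* Mean dissimilarity between individuals measures spread. If everyone in an arm moved the same way, the spread could stay the same.

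Neither number addresses direction. That leaves the plot of up to 30 × 2 = 60 samples, and the error rate of reading it is undefined.

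**3. Is a valid test feasible at this size?** With 15 per arm there are C(30,15) = 155,117,520 allocations. Restricting shuffles to age strata leaves ample room. If the subset split 15 and 15 by age (an assumption; the documents do not give the split), with arms 8/7 and 7/8, the count is C(15,7)² = 6,435² = 41,409,225.

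A null simulation of PERMANOVA tried this with one sample per participant, 15 per arm, simulated compositions of 40 taxa, Bray-Curtis distances, 199 unrestricted permutations and 600 runs. It rejected 5.3% of the time at a nominal 5%. The Monte Carlo standard error is √(0.05 × 0.95/600) = 0.9 points. The compositions are assumed, so this shows feasibility only.

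**4. What could one distance per participant detect?** For two-sided 5% and 80% power at 15 per arm, the normal approximation gives (1.960 + 0.842) × √(2/15) = 2.802 × 0.365 = 1.02 standard deviations. Using the t distribution on 28 degrees of freedom, it is about 1.06.

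**5. Three metrics.** Testing each at 0.05 gives a family-wise error of 1 − 0.95³ = 14.3% if the tests are independent, and less if they are correlated. A Bonferroni split (0.05/3 = 0.0167) raises the detectable difference to (2.394 + 0.842) × 0.365 = 1.18 by the normal approximation. Naming one lead metric avoids that cost.

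**6. A trap to avoid.** Fifteen people give 15 × 14/2 = 105 pairwise distances per arm, and these are not independent. Simulated t-tests on 105 against 105 Bray-Curtis distances, with no true difference and log-normal abundances (2,000 trials), rejected 46.3% of the time with 20 taxa and 47.4% with 60. Other spreads and numbers of taxa gave roughly 35% to 51%. The plan does not prescribe this test; the figure only shows why it should not be used to fill the gap.

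**The case against.** The strongest reply is that this is unpowered exploratory work in 30 people and that descriptive ordination is a defensible choice for it. Beta diversity is not named in the stated hypothesis, and the B:F ratio, the only microbiota measure with a power claim, does have a between-arm test. This stands, and it keeps the severity low. It does not remove the gap, because 7.2 goes beyond description when it says the plot helps distinguish directed change from noise.

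A reader might infer that beta diversity is to be judged by eye alone. The documents do not say that. Three numerical indices are computed, one of them a paired, within-person quantity, and the plot is worded as an aid. What remains is that nothing else is specified to settle direction or to compare the arms.

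A reader might also take 46–47% as the plan's own false-positive rate. It is not: it belongs to a t-test that the plan never mentions.

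A last objection is that participant-level distances do not by themselves answer the question of direction. That is correct. In an illustrative simulation (40 taxa, 15 per arm), one arm shifted in a common direction and the other by equal-sized moves in random directions. A t-test on own-baseline distances rejected only about 21% of the time. The remedy therefore needs a separate component for direction.

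**Conclusion.** The point holds in limited form. Section 3.2 lists the endpoint, and section 7.2 gives it summaries and a visual aid but no between-arm comparison and no error rate. As written, the plan cannot say whether composition changed more on treatment than on placebo. This rests on the text and on no simulated figure.

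The importance is low, since neither the SRS-2 conclusion nor participant safety is affected. The placement under Primary Safety Endpoints does not make this a primary question: sections 2, 7.1 and 7.2 call it exploratory, and the passages should be reconciled. Even with a valid test, a null result would say little. The detectable difference of about 1.06 standard deviations assumes 15 participants per arm with usable samples at both visits and a roughly normal distance measure.

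**What to change.** In section 7.2, keep the PCoA plot as illustration and base the between-arm inference on permutation, shuffling arm labels across whole participants within age stratum.

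1. **Directed shift.** Run PERMANOVA with Weighted Unifrac as lead metric and Bray-Curtis and Unweighted Unifrac as supportive. Use both visits and test the arm-by-time term, keeping each participant's two samples together. Alternatively, compare arms at Week 12 and report the same test at Baseline beside it. In either case add a dispersion check, so that a difference in spread is not read as a shift.
2. **Size of change.** Compare each participant's own Baseline-to-Week-12 distance between arms, and state that this does not by itself show direction.
3. **Limits.** Do not test the within-arm pairwise distances as if they were independent. Label the results exploratory, give the detectable difference, and align the heading in 3.2 with that status.

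The cost is a few sentences and some standard code, with no new samples or sequencing. It is best settled before the batched sequencing results are examined by arm. The downside is a little more analysis, and that a plot which looks separated may no longer be reported as a finding. If only description is wanted, the minimum is to say so and remove the claim about directed change and noise; the comparison with placebo would then stay unanswered.

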7.3 Subject Population(s) for Analysis

Study analysis will include all available data from all randomized subjects who received at least one dose of study medication and participated in at least one post-baseline efficacy assessment (i.e., intent-to-treat population). Missing outcome data will not be imputed and will be assumed to be missing at random.

8 Safety and Adverse Events

